5 STUDY ASSESSMENTS AND PROCEDURES

5.1 Flow Chart/Time and Events Schedule

Table 5.1-1: Screening Assessments (CA209139)		
Procedure	Screening Visit	Notes
Eligibility Assessments		
Informed Consent	X	
Inclusion/Exclusion Criteria	X	All inclusion/exclusion criteria should be assessed at screening, with confirmation of eligibility documented prior to first dose
Medical History	X	
Prior Systemic Therapy	X	
Safety Assessments		
Physical Examination	X	
Physical Measurements	X	Include Height, Weight, and ECOG Performance Status
Revised International Prognostic Index (IPI) at time of initial disease diagnosis	X	Refer to Appendix 3
Vital Signs and oxygen saturation	X	Temperature, BP, HR, O ₂ saturation by pulse oximetry (at rest and after exertion).
Assessment of Signs and Symptoms	X	Within 14 days prior to first dose
XXXXXXXXXX	X	Within 14 days prior to first dose
Laboratory Tests	X	CBC with differential, Chemistry panel including LDH, AST, ALT, ALP, T.Bili, BUN or serum urea level, uric acid, creatinine, Ca, Mg, Na, K, Cl, P, glucose, amylase, lipase TSH (reflex to free T3, free T4 for abnormal TSH result), hepatitis B surface antigen (HBV sAg), and hepatitis C antibody (HCV Ab) or HCV ribonucleic acid (RNA) within 14 days prior to first dose.
Urinalysis	X	Total protein, glucose, blood, leukocyte esterase, specific gravity, and pH, within 14 days prior to first dose
Pregnancy Test	X	

Table 5.1-2: On Treatment Assessments (CA209139)				
Procedure	Cycle 1 Day 1	Cycle 1 Day 8	Each cycle within 3 days prior to dosing	Notes
Safety Assessments				
Targeted Physical Examination	X		X	Lymph node areas (eg, submandibular, cervical, supraclavicular, axillary, or inguinal lymph node), and abdominal organs (eg, spleen)
Vital Signs and Oxygen Saturation	X	X	X	Temperature, BP, HR, RR, O2 saturation by pulse oximetry at rest and after exertion (also monitor amount of supplemental oxygen if applicable) prior to dosing and at any time a subject has any new or worsening respiratory symptoms
Adverse Events Assessment	X	X	X	Assessed using NCI CTCAE v. 4.0
	X	X	X	
Physical Measurements	X	X	X	Includes Weight and ECOG status
Laboratory Tests	X	X	X	extended on-treatment local laboratory assessments should be done within 72 hours prior to dosing for Cycle 1 through Cycle 5, and every alternate dose thereafter (Cycle 7, 9, 11, 13 etc) and include: CBC with differential, uric acid, serum urea level, serum creatinine, sodium, potassium, calcium, magnesium, phosphate, chloride, amylase, lipase, glucose, AST, ALT, total bilirubin, alkaline phosphatase, LDH. limited on-treatment local laboratory assessments should be done within 72 hours prior to dosing (beginning at Cycle 6 and every alternate dose thereafter (Cycle 8, 10, 12, 14 etc) and include: CBC with differential, LFTs (ALT, AST, total bilirubin, alkaline phosphatase) and creatinine.

Table 5.1-2: On Treatment Assessments (CA209139)				
Procedure	Cycle 1 Day 1	Cycle 1 Day 8	Each cycle within 3 days prior to dosing	Notes
				

 

 

Clinical Drug Supplies				
Administer Study Drug	X		X	IVRS should be called within 1 day prior to study drug administration to receive vial assignment

Table 5.1-3: Follow-up Assessments (CA209139)			
Procedure	Follow Up, Visits 1 and 2^a (X01 & X02)	Survival Follow-Up Visits^b	Notes
Safety Assessments			
Targeted Physical Examination	X		Lymph node areas (eg, submandibular, cervical, supraclavicular, axillary, or inguinal lymph node), and abdominal organs (eg, spleen) To assess for potential late emergent study drug related issues
Adverse Events Assessment	X	X	
Laboratory Tests	X		CBC with differential, uric acid, serum urea level, serum creatinine, sodium, potassium, calcium, magnesium, chloride, glucose, AST, ALT, total bilirubin, alkaline phosphatase, LDH, TSH (reflex to free T3, free T4 for abnormal TSH result)
Pregnancy Test (WOCBP only)	X		Serum or urine
GVHD Assessments	See note	See note	Only for subjects who discontinued study therapy by proceeding to allogeneic SCT. To be assessed on Day 100, at 6 months, at 1 year and every one year thereafter from the date of stem cell infusion until the first non-CR after SCT is documented. See Section 5.3

Table 5.1-3: Follow-up Assessments (CA209139)			
Procedure	Follow Up, Visits 1 and 2^a (X01 & X02)	Survival Follow-Up Visits^b	Notes
Efficacy Assessments			
Spiral CT/MRI	X	X	Only for subjects without progression on study therapy. 
 Tumor assessments should occur at the same intervals described in the Treatment Phase until disease progression, lost to follow-up, or withdrawal of study consent. Spiral CT or MRI chest, abdomen, pelvis and all known sites of disease. Use same imaging method as was used at screening/baseline.
PET scan			PET scan required to confirm CR.
Investigator tumor assessment for subjects receiving subsequent allogeneic SCT or ASCT	See note	See note	Only for subjects who discontinued study therapy by proceeding to allogeneic SCT or ASCT. To be assessed on Day 100, at 6 months, at 1 year and every one year thereafter from the date of stem cell infusion until the first non-CR after SCT is documented. See Section 5.4
[REDACTED]			
[REDACTED]	█		
[REDACTED]	█	█	[REDACTED]
[REDACTED]			
[REDACTED]	[REDACTED]		[REDACTED]

Table 5.1-3: Follow-up Assessments (CA209139)			
Procedure	Follow Up, Visits 1 and 2^a (X01 & X02)	Survival Follow-Up Visits^b	Notes
[REDACTED]			
[REDACTED]	■		[REDACTED]
Subject Status			
Survival Status	X	X	Every 3 months after X02; may be accomplished by visit, phone contact or email, to update survival information and assess subsequent anti-cancer therapy

^a Follow-up visit 1 (X01) = 35 days from the last dose +/- 7 days. Follow-up visit 2 (X02) = 80 days (+/- 7 days) from follow-up visit X01.

^b Survival Follow-up visits to occur every 3 months from X02

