- Subjects who discontinue study therapy for reasons other than disease progression or to receive an allogeneic or autologous stem cell transplant, will continue to have radiographic assessments at the intervals described in the Treatment Phase until disease progression, lost to follow-up, or withdrawal of study consent.
- For subjects who discontinue study therapy by proceeding to allogeneic SCT or ASCT, tumor assessment by the investigator will be required after allogeneic SCT or ASCT (see [Section 3.6](#)). For the subjects who discontinue study therapy by proceeding to allogeneic SCT, acute and chronic GVHD documentation will also be simultaneously collected (see [Section 5.3](#)).
- After completion of the two follow-up visits for safety, subjects will be followed every 3 months for survival, until death, lost to follow-up or withdrawal of study consent.
- QoL tools will be completed according to the schedule in [Table 5.1-3](#)

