3.6 Post Treatment Study Follow up

In this study, ORR and DOR are key endpoints of the study. Post treatment study follow-up is of critical importance and is essential to preserving subject safety and the integrity of the study. Subjects who discontinue study treatment must continue to be followed for collection of outcome and/or survival follow-up data as required and in line with [Section 5](#) until death or the conclusion of the study.

In addition, subjects who discontinue study therapy by proceeding to allogeneic SCT or ASCT will require tumor assessment (CR or non-CR) by the investigators according to the 2007 IWG criteria on Day 100, at 6 months, 1 year and every year thereafter from the date of stem cell infusion until the first non-CR after SCT is documented (see [Section 5.4](#)). For the subjects who discontinue study therapy by proceeding to allogeneic SCT, documentation of acute and chronic GVHD will be simultaneously collected (see [Section 5.3](#)).

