4.3.8.3 Discontinuation due to further progression

Subjects should discontinue study therapy upon evidence of further progression, defined as an additional 10% or greater increase in tumor burden volume from time of initial progression (including all target lesions and new measurable lesions).

- Further progression is evaluated by a subsequent CT or MRI which is performed at least 8 weeks from previous CT or MRI.
- The tumor burden volume from time of initial progression should be used as the reference baseline for comparison with the post-progression assessment.
- New lesions are considered measurable at the time of initial progression if the long axis is more than 15 mm regardless of the short axis. If a lymph node has a long axis of 11 to 15 mm, it should only be considered measurable if its short axis is more than 10 mm.
- Any new lesion considered non-measurable at the time of or after initial progression may become measurable and therefore included in the tumor burden determination.

4.3.8.4 Radiographic assessment for subjects who discontinue study drug during post-progression treatment

For subjects that discontinue post-progression treatment, no additional radiographic assessments will be required. Upon treatment discontinuation, these subjects will continue in the follow-up phase of the study (see [section 5.1](#)). Subjects who proceed to allogeneic SCT or ASCT will be followed as described in [Section 5.4](#).

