Some of the previously referred to assessments may not be captured as data in the eCRF. They are intended to be used as safety monitoring by the treating physician. Additional testing or assessments may be performed as clinically necessary or where required by institutional or local regulations.

For subjects who discontinue study therapy by proceeding to allogeneic SCT, documentation of acute and chronic GVHD will be captured on **Day 100, at 6 months, 1 year and every year thereafter from the date of stem cell infusion** until the first non-CR after SCT is documented [Appendix 5]. Investigators will make telephone contact with the subject's hematologist /oncologist /transplant physician to obtain this information if the subject is being followed by another physician.

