6.1.1 Serious Adverse Event Collection and Reporting

Following the subject's written consent to participate in the study, all SAEs, whether related or not related to study drug, must be collected, including those thought to be associated with protocol-specified procedures. All SAEs must be collected that occur during the screening period and within 100 days of discontinuation of dosing. If applicable, SAEs must be collected that relate to any later protocol-specified procedure (eg, a follow-up skin biopsy).

The investigator should report any SAE that occurs after these time periods and that is believed to be related to study drug or protocol-specified procedure.

An SAE report should be completed for any event where doubt exists regarding its seriousness.

If the investigator believes that an SAE is not related to study drug, but is potentially related to the conditions of the study (such as withdrawal of previous therapy or a complication of a study procedure), the relationship should be specified in the narrative section of the SAE Report Form.

SAEs, whether related or not related to study drug, and pregnancies must be reported to BMS (or designee) within 24 hours. SAEs must be recorded on the SAE Report Form; pregnancies on a Pregnancy Surveillance Form (electronic or paper forms). When using paper forms, the reports are to be transmitted via email or confirmed facsimile (fax) transmission to:

SAE Email Address: Refer to Contact Information list.

SAE Facsimile Number: Refer to Contact Information list.

For studies capturing SAEs through electronic data capture (EDC), electronic submission is the required method for reporting. The paper forms should be used and submitted immediately, only in the event the electronic system is unavailable for transmission. When paper forms are used, the original paper forms are to remain on site.

SAE Telephone Contact (required for SAE and pregnancy reporting): Refer to Contact Information list.

If only limited information is initially available, follow-up reports are required. (Note: Follow-up SAE reports should include the same investigator term(s) initially reported.)

If an ongoing SAE changes in its intensity or relationship to study drug or if new information becomes available, a follow-up SAE report should be sent within 24 hours to the BMS (or designee) using the same procedure used for transmitting the initial SAE report.

All SAEs should be followed to resolution or stabilization.

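### Scheduled GVHD documentation depends on why nivolumab was stopped, not on receipt of an allogeneic transplant after it, so GVHD after later transplants reaches the database only through general AE and SAE reporting

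*Protocol*

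**What the plan says.** Four places in the protocol set who is documented for GVHD, and they agree.

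- Table 5.1-3, GVHD Assessments row: "Only for subjects who discontinued study therapy by proceeding to allogeneic SCT".
- Section 3.1, Follow-Up Phase: "For the subjects who discontinue study therapy by proceeding to allogeneic SCT, acute and chronic GVHD documentation will also be simultaneously collected".
- Section 3.6: "For the subjects who discontinue study therapy by proceeding to allogeneic SCT, documentation of acute and chronic GVHD will be simultaneously collected".
- Section 5.3: "For subjects who discontinue study therapy by proceeding to allogeneic SCT, documentation of acute and chronic GVHD will be captured on". The schedule it sets counts from stem cell infusion: Day 100, then 6 months, 1 year and yearly.

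The Synopsis is in line: it speaks of subjects who discontinue in order to receive a transplant. GVHD follow-up in covered subjects runs "until the first non-CR after SCT is documented".

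Section 4.3.8.4, on subjects who stop during post-progression treatment, says: "Subjects who proceed to allogeneic SCT or ASCT will be followed as described in". The place it names is Section 5.4, which covers tumor status. It also sends these subjects to the follow-up phase in Section 5.1.

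For all treated subjects, Section 6.1.1 requires every SAE to be collected "within 100 days of discontinuation of dosing", and later SAEs only if believed related to study drug or a protocol procedure. Section 6.2.1 requires nonserious AEs for at least 100 days after the last dose. Table 5.1-3 marks AE assessment at survival visits and uses the 3-monthly contact "to update survival information and assess subsequent anti-cancer therapy".

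**The concern.** GVHD after nivolumab can arise in anyone who had the drug and then an allogeneic graft. Entry to the scheduled GVHD record is instead decided by the reason for stopping. Progression, toxicity and the start of a preparative regimen are separate reasons in Sections 3.5 and 4.3.5. A subject who stops for one of the first two and is transplanted afterwards does not, on the plain wording, discontinue by going to transplant.

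At stake is the completeness of the post-transplant safety data. Any summary of GVHD would describe subjects taken from nivolumab to transplant and leave out those who first stopped for progression or toxicity. Because the governing phrase is undefined, two sites could also classify the same subject differently.

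**Working it through.** No stated sample size, power or error rate is in question. The check is a comparison of text, plus the timing of the reporting windows.

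**Who is covered**

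| Place | Population |
|---|---|
| 3.1, 3.6, 5.3, Table 5.1-3 GVHD row | Stopped nivolumab by going to allogeneic SCT |
| 5.4, Table 5.1-3 tumor row note (CR/non-CR) | Stopped nivolumab by going to allogeneic SCT or ASCT |
| Table 5.1-3 tumor row title | Receiving a subsequent allogeneic SCT or ASCT |
| 4.3.8.4 | Left post-progression treatment, then SCT: cites 5.4 and 5.1, not 5.3 |

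No visible text extends the GVHD schedule to a subject who stops for another reason and is transplanted later. The tumor row's title is wider than its own note, which adds to the uncertainty over who is meant.

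**What general safety reporting covers.** Let t be the days from last dose to stem cell infusion.

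- All-cause collection remaining after infusion = 100 − t days. At t = 60 this is 40 days, at t = 90 it is 10 days, and at t ≥ 100 it is none.
- The first scheduled GVHD time point is Day 100 after infusion, which is day 100 + t after the last dose. For any t > 0 this lies outside the 100-day window.
- X01 is 35 ± 7 days after the last dose, so days 28 to 42. X02 is 80 ± 7 days after X01, so from 28 + 73 = 101 to 42 + 87 = 129 days (nominal 35 + 80 = 115).
- After X02, Section 3.1 describes 3-monthly follow-up of ongoing drug-related AEs. The AE mark at survival visits carries no GVHD-specific item.

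Beyond day 100, then, reporting turns mainly on a judgement that the event is drug-related. GVHD has an evident alternative cause in the graft, so that filter suits it poorly. AE summaries also use CTCAE grades (Section 8.4.3), whereas Appendix 5 stages acute GVHD by organ and chronic GVHD as limited or extensive. The two sources would not combine cleanly.

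**Is the route foreseeable?** The ASCT-failed cohort is powered at a true ORR of 35%, so even then 100% − 35% = 65% would not respond. Progression requires stopping apart from the exception in 4.3.8. How many such subjects later receive an allograft is not given.

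**Is the drug still present?** Section 3.3.1 gives 23 weeks (161 days) as five half-lives plus 30 days, and 31 weeks (217 days) as five half-lives plus 90 days. The implied half-life is (161 − 30)/5 = 26.2 days or (217 − 90)/5 = 25.4 days. Assuming simple first-order elimination, the fraction left at 60 days is 2^(−60/25.4) = 0.19 to 2^(−60/26.2) = 0.20, and at 90 days 0.086 to 0.092. Later transplants still follow real exposure, but at a level that falls with the interval.

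**Dependency on tumor status.** GVHD follow-up ends at the first non-CR after transplant. CR/non-CR is assessed only in the same restricted group, and Table 5.1-3 limits CT/MRI in follow-up to subjects without progression. Widening the GVHD population alone would leave the added subjects with a stopping event that nobody is required to assess.

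**The case against.** The strongest reply is that the protocol does not leave these subjects unobserved. A reader might infer that they have no GVHD follow-up at all, and that goes too far. All-cause AEs and SAEs are collected to 100 days, later SAEs if believed related, and AE assessment is marked at survival visits. What is missing is scheduled, structured documentation.

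Three other inferences also fail.

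- *The omitted subjects had the same drug exposure.* The documents support only prior exposure. Number of doses and interval to transplant can differ, and the half-life arithmetic shows the residual level falling.
- *Section 4.3.8.4 excludes them from GVHD follow-up.* It is a section on radiographic assessment, so citing 5.4 is natural, and it also points to 5.1, which holds the GVHD row. It is silent on coverage and does not exclude anyone.
- *A planned GVHD analysis has the wrong denominator.* No visible objective, endpoint or SAP analysis concerns GVHD. Parts are redacted, and SAP 7.6 defers to a Core Safety SAP that is not part of these documents.

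One could also defend the restriction because GVHD after a long interval and other therapy is hard to attribute to nivolumab. That is plausible, though the protocol does not say so. Reporting by interval from last dose deals with it better than not collecting the data.

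What survives is that coverage follows the stopping reason, in four consistent places, through an undefined phrase.

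**Conclusion.** The point holds as a limited one. Scheduled acute and chronic GVHD documentation is tied to the reason for stopping nivolumab, and later allogeneic transplants rely on general reporting whose all-cause part shrinks day for day with the interval and is gone by day 100. The resulting GVHD data are selected by stopping reason.

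The size in subjects cannot be derived: the documents give neither an allogeneic transplant rate nor a split by stopping reason, so any count would be pure assumption. Whether GVHD risk differs between the groups is likewise not something the documents show. The primary ORR analysis is untouched. The conclusion rests on the visible text, and redacted sections could contain further GVHD provisions. It is a worthwhile, inexpensive improvement to safety data collection, with no effect on the efficacy conclusions.

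**What to change.** 1. In Protocol 3.1, 3.6, 5.3 and the GVHD row of Table 5.1-3, define the population as every subject who receives an allogeneic SCT after any dose of nivolumab, whatever the reason for discontinuation.
2. Make the same change for allogeneic SCT recipients in the CR/non-CR assessment in 3.1, 3.6, 5.4 and the tumor row of Table 5.1-3, because GVHD follow-up ends on that assessment.
3. In 4.3.8.4, cite 5.3 alongside 5.4.
4. Identify these subjects through the existing 3-monthly contact, which already asks about subsequent anti-cancer therapy.
5. Report GVHD by stopping reason and by interval from last dose to transplant.

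The cost is amendment wording and a few extra telephone contacts with transplant physicians, a route that 5.3 and 5.4 already provide. No new tests are needed. The drawback is that GVHD after a longer interval or intervening therapy is harder to attribute, which is why step 5 separates it.

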5.2 Study Materials

The following materials will be provided at study start:

- NCI CTCAE version 4.0
- BMS-936558 (nivolumab) Investigational Brochure
- Pharmacy Binder
- Laboratory manuals for collection and handling of blood (including PKs, biomarker and immunogenicity) and tissue specimens
- Site manual for operation of interactive voice response system (IVRS)
- Manual for entry of local laboratory data
- Serious Adverse Event (or eSAE) case report forms
- EQ-5D and EORTC QLQ-C30 questionnaires
- Pregnancy Surveillance Forms
- IRRC manual

5.3 Safety Assessments

At baseline, a medical history will be obtained to capture relevant underlying conditions. The baseline examinations should include weight, height, ECOG Performance Status, BP, HR, temperature, and oxygen saturation by pulse oximetry at rest and after exertion should be performed within 28 days prior to first dose. Baseline signs and symptoms are those that are assessed within 14 days prior to first dose. Concomitant medications will be collected from within 14 days prior to the first dose through the study treatment period (see [Table 5.1-1](#)).

Baseline local laboratory assessments should be done within 14 days prior to first dose to include: CBC w/differential, LFTs (ALT, AST, total bilirubin, alkaline phosphatase), uric acid, BUN or serum urea level, creatinine, Ca, Mg, Na, K, Cl, P, LDH, amylase, lipase glucose, urinalysis, TSH, and Hep B and C testing (HBV sAg, HCV Ab, or HCV RNA) (see [Table 5.1-1](#)). Pregnancy testing for WOCBP (done locally) must be performed at baseline (within 28 days prior to first dose) and repeated within 24 hours prior to the initial administration of study drug, then every 4 weeks (\pm 7 days) regardless of dosing schedule.

Subjects will be evaluated for safety if they have received any study drug. Toxicity assessments will be continuous during the treatment phase. During the safety follow-up phase (Follow-up visits X01 and X02, [Table 5.1-3](#)) toxicity assessments should be done in person. Once subjects reach the survival follow-up phase, either in-person visits or documented telephone calls/email correspondence to assess the subject's status are acceptable.

Adverse events and laboratory values will be graded according to the NCI-CTCAE version 4.0.

On-study weight, ECOG performance status, and vital signs should be assessed at each on-study visit prior to nivolumab dosing and at Cycle 1 Day 8. Vital signs should also be taken as per institutional standard of care prior to, during and after dosing. Oxygen saturation by pulse oximetry at rest and after exertion should be assessed at each on-study visit prior to nivolumab

dosing. The start and stop time of the nivolumab infusion should be documented. Physical examinations are to be performed as clinically indicated. If there are any new or worsening clinically significant changes since the last exam, report changes on the appropriate non-serious or serious adverse event page.

On treatment local laboratory assessments should be done within 72 hours prior to dosing;

- **Extended on-treatment local laboratory assessments:** Cycle 1 (including day 1 and day 8) through Cycle 5 and every alternate dose thereafter (Cycle 7, 9, 11, 13 etc) and include: CBC with differential, uric acid, serum urea level, serum creatinine, sodium, potassium, calcium, magnesium, phosphate, chloride, amylase, lipase, glucose, AST, ALT, total bilirubin, alkaline phosphatase, LDH.
- **Limited on-treatment laboratory assessments:** beginning at Cycle 6 (week 11) and every alternate dose thereafter (Cycle 8, 10, 12, 14 etc) and include: CBC, LFTs (ALT, AST, total bilirubin, alkaline phosphatase) and creatinine.

In addition, TSH (with reflexive testing to free T3, free T4 for abnormal TSH result) should be performed every 6 weeks (\pm 7 days) regardless of dosing schedule.

Additional measures, including non-study required laboratory tests, should be performed as clinically indicated or to comply with local regulations. Laboratory toxicities (eg, suspected drug induced liver enzyme elevations) will be monitored during the follow-up phase via on site/local labs until all study drug related toxicities resolve, return to baseline or are deemed irreversible.

Oxygen saturation by pulse oximetry should be obtained prior to each dose of nivolumab and at any time a subject has any new or worsening respiratory symptoms. A reading at rest and on exertion should be obtained at each time point. The extent of the exertion should be based on the judgment of the investigator, but should remain consistent for each individual subject throughout the study. If the patient's subject's status changes, the investigator can alter the extent of exertion based on their medical judgment. If a subject shows changes on pulse oximetry or other pulmonary-related signs (eg, hypoxia, fever) or symptoms (eg, dyspnea, cough) consistent with possible pulmonary adverse events, the patient subject should be immediately evaluated to rule out pulmonary toxicity. An algorithm for the management of suspected pulmonary toxicity can be found in [Appendix 1](#) and the BMS-936558 (nivolumab) Investigator Brochure.

Some of the previously referred to assessments may not be captured as data in the eCRF. They are intended to be used as safety monitoring by the treating physician. Additional testing or assessments may be performed as clinically necessary or where required by institutional or local regulations.

For subjects who discontinue study therapy by proceeding to allogeneic SCT, documentation of acute and chronic GVHD will be captured on **Day 100, at 6 months, 1 year and every year thereafter from the date of stem cell infusion** until the first non-CR after SCT is documented [Appendix 5]. Investigators will make telephone contact with the subject's hematologist /oncologist /transplant physician to obtain this information if the subject is being followed by another physician.

